## LIST OF ABBREVIATIONS

ADF	Alternate day fasting
BIA	Bioelectrical Impedance analysis
CRP	C-Reactive Protein
DXA	Dual-energy X-ray Absorptiometry
FGF-21	Fibroblast growth factor-21
IL-6	Interleukin-6
MRS	Magnetic resonance spectroscopy
NAFLD	Non-alcoholic fatty liver disease
OGGT	Oral glucose tolerance test
PI	Principal investigator
RBP4	Retinol binding protein 4
SHBG	Sex hormone binding globulin
TNF-a	Tumor necrosis factor-alpha

## 1.0 Project Summary/Abstract

**Background:** Approximately 65% of obese individuals have non-alcoholic fatty liver disease (NAFLD), and this condition is strongly related to the development of insulin resistance and diabetes. Innovative lifestyle strategies to treat NAFLD are critically needed. Alternate day fasting (ADF) has been shown in animals to reduce hepatic steatosis and improve hepatic insulin sensitivity, but these findings have yet to be confirmed in human subjects. ADF consists of a “feast day” where individuals are permitted to consume food *ad libitum*, alternated with a “fast day” where individuals consume 25% of their usual intake (~500 kcal). We performed a pilot study to evaluate the effects of ADF combined with exercise, versus ADF or exercise alone, on hepatic parameters in obese patients. Our results show that the combination of ADF plus exercise produced greater reductions in alanine aminotransferase (ALT; an indirect marker of hepatic steatosis), compared to ADF alone, or exercise alone, after 12 weeks. Greater decreases in insulin resistance, HbA1c, LDL cholesterol, and more pronounced increases in HDL cholesterol, were observed in the combination group versus individual interventions. Data from our pilot trial also suggest that these decreases in insulin resistance may be mediated in part by changes in hepatocyte-derived hormones (hepatokines) that occur with liver fat reduction. Although these pilot findings are very promising, these data still require confirmation by a well powered longer-term (24 week) clinical trial.

**Hypotheses:** The present proposal will test the following hypotheses: **(1)** The combination group (ADF plus exercise) will experience greater reductions in hepatic steatosis (measured by magnetic resonance spectroscopy; MRS) when compared to ADF or exercise alone; **(2)** The combination group will experience greater improvements in hepatokine profile (fetuin-A, fetuin B, FGF-21, RBP4, selenoprotein P, SHBG, adiponectin) when compared to ADF or exercise alone; **(3)** The combination group will experience greater improvements in hepatic insulin sensitivity, insulin resistance and HbA1c and other metabolic disease risk variables (fasting glucose, fasting insulin, triglycerides, LDL cholesterol, blood pressure, inflammatory parameters) when compared to ADF or exercise alone. **Methods:** To test these objectives, a 24-week randomized, controlled, parallel-arm feeding trial will be implemented. Obese individuals with NAFLD (n = 360) will be randomized to 1 of 4 groups: (1) ADF (fast day: 25% energy intake, feed day: *ad libitum* fed, no exercise), (2) exercise (*ad libitum* fed, training 5 days/week), (3) combination (ADF plus exercise), and (4) control (*ad libitum* fed, no exercise). **Significance:** If the aims of this application are achieved, this study will be the first to show that the combination of alternate day fasting plus aerobic exercise is an effective non-pharmacological therapy to reduce hepatic steatosis, improve hepatic insulin sensitivity and prevent the progression to type 2 diabetes in NAFLD patients.

## 2.0 Background/ Scientific rationale

Nonalcoholic fatty liver disease (NAFLD) is characterized by an accumulation of fat in the liver (not resulting from excessive alcohol consumption). Approximately 65% of obese individuals have NAFLD, and this condition is strongly related to the development of insulin resistance and type 2 diabetes. While certain pharmacological agents have been shown to reduce liver fat (i.e. thiazolidinediones), there is mounting concern regarding the safety and weight-gaining effects of these compounds. In light of this, recent research has focused on non-pharmacological lifestyle therapies to reduce hepatic steatosis, such as daily calorie restriction combined with aerobic exercise. Evidence from clinical trials suggest that this combination is an effective lifestyle therapy to improve liver fat content and hepatic insulin sensitivity.

More recently, it's been shown that intermittent fasting may produce even greater improvements in hepatic steatosis and hepatic insulin sensitivity, when compared to conventional calorie restriction. For instance, intrahepatic lipid accumulation was lower and insulin sensitivity was higher in mice fasted every other day, when compared to mice who were energy restricted every day. Moreover, data from human trials show that obese adults experience greater decreases in insulin and insulin resistance with intermittent fasting versus daily restriction. These findings suggest that intermittent fasting may be a more effective diet therapy to reduce hepatic steatosis and improve insulin sensitivity, when compared to daily calorie restriction.

We recently performed a pilot study to evaluate the effects of alternate day fasting (ADF) and exercise, alone or combined, on various hepatic parameters in obese adults. ADF consists of a "fast day", in which 25% of energy needs (~500 kcal) are consumed, alternated with a "feed day", in which food is consumed ad libitum. Results from our pilot study show that the combination of ADF plus exercise produced greater reductions (-21 ± 9%) in alanine aminotransferase (ALT; an indirect marker of hepatic steatosis), compared to ADF alone (-13 ± 4%), or exercise alone (-16 ± 7%) after 12 weeks. Greater decreases in insulin resistance, HbA1c, LDL cholesterol, and more pronounced increases in HDL cholesterol, were observed in the combination group versus individual interventions. Data from our pilot trial also suggest that these decreases in insulin resistance by ADF plus exercise may be mediated in part by changes in hepatocyte-derived hormones (fetuin-A and FGF-21) that occur with liver fat reduction. Although these pilot findings are very promising, these data still require confirmation by a larger-scale (n = 360), longer-term (24 week) clinical trial. Accordingly, the specific aims of this study are:

## 3.0 Objective/Aims

**Specific aim 1:** To compare the effects of a combination intervention (ADF and aerobic exercise) versus ADF or exercise alone on hepatic steatosis over 24-weeks in prediabetic obese NAFLD subjects.

**Hypothesis 1:** The combination group will experience greater reductions in hepatic steatosis (measured by MRS) when compared to the ADF group and the aerobic exercise group.

**Specific aim 2:** To compare the effects of a combination intervention (ADF and aerobic exercise) versus ADF alone or aerobic exercise alone on hepatokine profile over 24-weeks in prediabetic obese NAFLD subjects.

**Hypothesis 2:** The combination group will experience greater decreases in hepatokines with negative metabolic actions (fetuin-A, fetuin B, FGF-21, RBP4, selenoprotein P) and greater increases in hepatokines with positive metabolic actions (SHBG, adiponectin) when compared to the ADF group and the exercise group.

**Specific aim 3:** To compare the effects of a combination intervention (ADF and aerobic exercise) versus ADF alone or aerobic exercise alone on hepatic insulin sensitivity, insulin resistance, HbA1c, and other metabolic disease risk variables over 24-weeks in prediabetic-obese NAFLD subjects.

**Hypothesis 3:** The combination group will experience greater improvements in hepatic insulin sensitivity, insulin resistance and HbA1c and other metabolic disease variables (fasting glucose, insulin, plasma lipids, blood pressure, TNF- $\alpha$ , IL-6) when compared to the ADF group and the exercise group.

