### 4.1 Inclusion criteria:

- Age between 18 to 65 years old
- BMI between 30.0 and 59.9 kg/m^2
- NAFLD (hepatic steatosis  $\geq$  5% previously diagnosed) and ALT  $>$  15 U/L
- Prediabetic (fasting glucose: 100-125 mg/dl, HbA1c: 5.7-6.4%) or normoglycemic (fasting glucose:  $<$ 100 mg/dl, HbA1c:  $<$ 5.7%) 
- Sedentary ( $<$ 20 min, 2x/week of light activity at 3-4 metabolic equivalents (METs) for 3 mo prior to study) 

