**Hepatic insulin sensitivity by OGTT and Matsuda Index:** Hepatic insulin sensitivity will be assessed at week 1, 13 and 24 by the oral glucose tolerance test (OGTT) and Matsuda Composite Index. For this procedure, subjects will arrive at the research center in the morning after a 12-h fast. They will have their blood drawn (20 ml), and then be given a 75 g dose of glucose (Thermo Scientific Glucose Tolerance Test Beverage, Waltham, MA). Four blood samples (20 ml each) will be taken 30, 60, 90, and 120 min after the glucose dose for the measurement of glucose and insulin. Hepatic insulin sensitivity will be calculated as Matsuda's Insulin sensitivity index (ISI) = [10000/(fasting glucose x fasting insulin x mean glucose during OGTT x mean insulin during OGTT)1/2].

**Activity monitor:** All subjects will be instructed to maintain their regular daily activity habits (i.e not join a gym or participate in other exercise classes). Alterations in physical activity habits will be quantified by an activity monitor (Fitbit Alta HR, Boston, MA) that will be worn on the wrist for 7 days at week 1,13, and 24.

**Food record:** Dietary intake will be assessed in all groups by a 7-day food record at week 1, 13 and 24. Subjects will be given detailed guidelines on how to complete the records by the Dietician at baseline. Dietary intake data will be assessed by Nutritionist Pro software (Axxya, TX).

**Michigan Alcohol Screening test:** Alcohol consumption will be assessed by the Michigan Alcohol Screening Test at the screening appointment.

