**Metabolic disease risk factors:** Plasma metabolic disease risk factors will be assessed at baseline week 1, 13, and 24. Plasma total cholesterol, LDL cholesterol, HDL cholesterol, and triglyceride concentrations will be measured in duplicate using enzymatic kits, standardized reagents, and standards (Biovision Inc, Mountainview, CA) and analyzed using a microplate reader (iMark Microplate Reader; Bio-Rad Laboratories Inc, Richmond, CA). HbA1c will be assessed by ELISA (Mybiosource, San Diego, CA). Fasting plasma glucose concentrations will be measured with a hexokinase reagent kit in duplicate (A-agent glucose test, Abbott, South Pasadena, CA). Fasting insulin will be measured as total immunoreactive insulin (Coat-A-Count Insulin, Los Angeles, CA). Insulin resistance (IR) will be calculated by the HOMA (Homeostasis Model Assessment) method:  $[HOMA-IR = \text{Fasting insulin } (\mu\text{U/ml}) \times \text{Fasting glucose } (\text{mg/dL}) / 405]$ .

**Proteomics and metabolomics:** Plasma-derived proteomic and metabolomic outcomes will be measured using immunoassay and mass spectrometry, as described previously.

**Hepatokine plasma levels:** Plasma hepatokines will be measured at week 1, 13, and 24. Commercially available ELISA kits will be used to measure concentrations of Fetuin-A, fetuin-B, FGF-21, SHBG, and RBP4, (R&D Systems, Minneapolis), and adiponectin and selenoprotein P (Mybiosource, San Diego, CA). All samples will be assessed in duplicate.

**Inflammation:** Inflammatory markers will be measured at week 1, 13, and 24. C-reactive protein (CRP) will be measured in duplicate using Immulite 1000 High Sensitivity CRP kits (Diagnostic Products Corporation, Los Angeles, CA). Adiponectin, leptin, TNF- $\alpha$ , and IL-6 will be measured using ELISA (R&D Systems, Minneapolis, MN).

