## 12.0 Statistical considerations

All continuous variables will be examined for distributions and the presence of outliers. Variables that are not normally distributed will be transformed and if normality cannot be achieved, will be analyzed using non-parametric tests. Standardized descriptive statistics including measures of means, median, standard deviations, ranges, and standard errors for continuous variables within each group will be calculated to describe the groups at fixed time points. Differences between groups at baseline will be assessed by a one-way ANOVA. A repeated measures ANOVA will be used to evaluate the effects of diet, exercise, and their interaction (diet x exercise) on dependent variables; a significant interaction will be interpreted with a Bonferroni correction for multiple comparisons. A multivariate analysis that adjusts for the effects of confounding variables (age, sex, race, and baseline hepatic steatosis, hepatic insulin sensitivity, hepatokine profile, body weight, and body composition) will also be performed. Relations between continuous variables will be assessed by Pearson's or Spearman's correlation coefficients as appropriate. Data will be analyzed using SPSS software (SPSS, Chicago, IL).

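### Aims 1-3 name prediabetic subjects, but eligibility also admits normoglycemic subjects and only pooled analyses are planned; separately, the covariate list lacks the baseline of HbA1c, fasting glucose and most other Hypothesis 3 outcomes

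*Combined protocol and SAP*

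**What the plan says.** **Population.** In Section 3.0, Aim 1 is a comparison "on hepatic steatosis over 24-weeks in prediabetic obese NAFLD subjects". Aim 2 uses the same population phrase, and Aim 3 covers metabolic "risk variables over 24-weeks in prediabetic-obese NAFLD subjects". The three hypotheses beneath the aims carry no glycemic restriction.

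The inclusion criterion in Section 4.1 is wider: "Prediabetic (fasting glucose: 100-125 mg/dl, HbA1c: 5.7-6.4%) or normoglycemic". Sections 1.0 and 6.0 describe the sample without glycemic status: "Obese individuals with NAFLD (n = 360) will be randomized to 1 of 4 groups".

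**Analysis.** Section 12.0 plans a repeated measures ANOVA (diet, exercise and their interaction), one covariate-adjusted multivariate analysis, and correlations. It has no prediabetic analysis set, no subgroup and no term for treatment by glycemic status. The adjusted analysis uses "age, sex, race, and baseline hepatic steatosis, hepatic insulin sensitivity, hepatokine profile, body weight, and body composition". The section does not say whether the outcome in that analysis is a change, a week 24 value or the repeated series.

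**Outcomes and measurement.** Hypothesis 3 expects "greater improvements in hepatic insulin sensitivity, insulin resistance and HbA1c and other metabolic disease variables (fasting glucose, insulin", and goes on to plasma lipids, blood pressure, TNF-alpha and IL-6. Section 6.0 states: "Plasma metabolic disease risk factors will be assessed at baseline week 1, 13, and 24". Blood pressure and the inflammatory markers follow the same three time points. On the covariate that reflects insulin sensitivity, Section 6.0 says: "Hepatic insulin sensitivity will be calculated as Matsuda's Insulin sensitivity index".

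**The concern.** Two issues arise, and they are separate.

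First, the aims name a population that no planned analysis isolates. If the result is reported in the words of the aims, an average over prediabetic and normoglycemic subjects will read as an effect in prediabetes. What is at stake is whom the conclusion describes.

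Second, the covariate list is uneven. It includes the baseline of the Aim 1 outcome (steatosis), the Aim 2 outcomes (hepatokines) and one Aim 3 outcome (hepatic insulin sensitivity). It leaves out the baseline of HbA1c and fasting glucose, the two laboratory values that define the admitted glycemic groups, and of the remaining Hypothesis 3 outcomes. Because the form of the adjusted model is not given, the reader cannot tell whether those week 1 values are used in some other way. What is at stake here is precision.

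**Working it through.** **Step 1: the population, section by section.** The plan gives no figure to reproduce on this point, so the check is a comparison of text.

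| Place | Population |
|---|---|
| 3.0, Aims 1-3 | Prediabetic, obese, NAFLD (3 of 3 aims) |
| 3.0, Hypotheses 1-3 | No glycemic restriction (0 of 3) |
| 1.0 and 6.0 | Obese with NAFLD |
| 4.1 | Prediabetic or normoglycemic |
| 12.0 | All groups pooled; no prediabetic estimate |

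The aims are the outlier. The other sections agree with one another.

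**Step 2: the covariate list against Hypothesis 3.** Hepatic insulin sensitivity has its own baseline on the list. HbA1c, fasting glucose, insulin, insulin resistance, lipids, blood pressure, TNF-alpha and IL-6 do not. The Matsuda formula contains fasting glucose and OGTT glucose, so it carries part of baseline glucose. HbA1c does not enter it.

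**Step 3: what an own-baseline covariate would gain.** Assumptions, none of them from the documents: two arms of n subjects, equal variance (set to 1) at weeks 1 and 24, and correlation ρ between them of 0.5, 0.7 or 0.9. The variance of the difference between arms at week 24 is:

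- week 24 value with week 1 as covariate: 2(1 − ρ²)/n
- change from week 1: 4(1 − ρ)/n
- week 24 value without week 1: 2/n

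The standard error with the covariate, relative to each alternative, is:

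- against change: √[2(1 − ρ²) / 4(1 − ρ)] = √[(1 + ρ)/2]
- against week 24 alone: √(1 − ρ²)

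| ρ | SE ratio vs change | CI narrower by | SE ratio vs week 24 alone | CI narrower by |
|---|---|---|---|---|
| 0.5 | √0.75 = 0.866 | 13.4% | √0.75 = 0.866 | 13.4% |
| 0.7 | √0.85 = 0.922 | 7.8% | √0.51 = 0.714 | 28.6% |
| 0.9 | √0.95 = 0.975 | 2.5% | √0.19 = 0.436 | 56.4% |

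n cancels, so the ratios do not depend on arm size. The two comparators move in opposite directions as ρ rises, so no single range describes the gain until the model form is stated.

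**Step 4: what a prediabetic-only estimate would cost.** This illustration assumes two-sided alpha 0.05, 80% power, SD = 1, the 90 per arm of Section 5.0, and a prediabetic share f, which the documents do not give. The detectable difference is (1.960 + 0.842) × √[2/(90f)]: 0.42 SD at f = 1, 0.48 SD at f = 0.75, 0.59 SD at f = 0.50 and 0.84 SD at f = 0.25.

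**The case against.** The strongest reply on the population is that nothing in the plan commits to a claim specific to prediabetes. The hypotheses, the abstract's significance statement and the design section all speak of NAFLD subjects in general, and randomization protects the pooled comparison. This stands, and it is why the point is minor. It does not remove the mismatch in the three aim sentences, which are what a report of the trial would be read against.

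One could also reconcile the text the other way, by adding a pre-specified prediabetic estimate. That is possible, but it is the weaker choice. Precision would fall by an amount that depends on an unstated share (step 4). Section 4.1 also does not say how a subject with discordant glucose and HbA1c is classified, so the subset is not clearly defined.

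On the covariates, the strongest reply is that HbA1c and glucose are measured at weeks 1, 13 and 24. A repeated measures model with week 1 as a level therefore already uses the baseline values. This stands as well. A reader might infer from the covariate list that baseline HbA1c and glucose are ignored altogether, but the documents do not support that, because Section 12.0 leaves the form of the adjusted model open. Nor is there reason to single out these two variables: insulin, insulin resistance, lipids, blood pressure, TNF-alpha and IL-6 are in the same position.

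**Conclusion.** The point holds and is minor. The aims name a narrower population than the one enrolled and analysed, and the pooled result does not estimate an effect in prediabetes.

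The covariate part is conditional. Adjusting each Hypothesis 3 outcome for its own week 1 value would narrow the 95% CI by about 13%, 8% or 3% (ρ = 0.5, 0.7, 0.9) if the planned model in effect analyses change, and by about 13%, 29% or 56% if it analyses week 24 values without week 1. These figures rest on assumed correlations and equal variances. They are smaller where listed covariates, such as the Matsuda index for glucose, already carry the baseline information.

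A reader might infer three stronger things, none of which the documents support:

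- **That the pooled comparison is invalid.** It is a randomized comparison and is valid for the mixed population.
- **That leaving out baseline HbA1c and glucose biases the treatment effect.** Under randomization the omission costs precision only.
- **That normoglycemic subjects dilute the HbA1c or glucose effects by a known amount.** Dilution is possible, but the documents give neither the prediabetic share nor effects by glycemic status, so it cannot be sized and none is claimed.

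**What to change.** 1. **Aims.** Restate Aims 1-3 for the population enrolled, for example obese NAFLD subjects with prediabetes or normoglycemia, and state that no prediabetes-specific conclusion will be drawn from the pooled analysis. Eligibility need not change for this.
2. **Adjusted model.** State its form in Section 12.0. For each Hypothesis 3 outcome, including HbA1c and fasting glucose, use that outcome's own week 1 value as a covariate with weeks 13 and 24 as the outcomes. Week 1 then leaves the outcome vector and is not used on both sides.

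**Cost.** The changes need new wording in the protocol and SAP and slightly more analysis work. No new measurements are needed, because the week 1 values are already scheduled. The conclusion can no longer read as specific to prediabetes. Subjects without a week 1 value drop out of the adjusted model for that outcome. The adjusted model will also differ in form from a repeated measures ANOVA that keeps week 1 as a level, and the report should say so.

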## 4.0 Eligibility

Subject eligibility will be assessed and determined by [name] M.S., R.D., or key research personnel identified in Appendix P. Screening will be conducted over Zoom and at the Human Nutrition Research Unit (HNRU) located in the Applied Health Sciences Building ([name]).

### 4.1 Inclusion criteria:

- Age between 18 to 65 years old
- BMI between 30.0 and 59.9 kg/m^2
- NAFLD (hepatic steatosis  $\geq$  5% previously diagnosed) and ALT  $>$  15 U/L
- Prediabetic (fasting glucose: 100-125 mg/dl, HbA1c: 5.7-6.4%) or normoglycemic (fasting glucose:  $<$ 100 mg/dl, HbA1c:  $<$ 5.7%) 
- Sedentary ( $<$ 20 min, 2x/week of light activity at 3-4 metabolic equivalents (METs) for 3 mo prior to study) 

### 4.2 Exclusion criteria:

- Have chronic liver disease other than NAFLD (hepatitis B or C, primary biliary cirrhosis, sclerosing cholangitis, autoimmune hepatitis, hemochromatosis, Wilson's disease,  $\alpha$ 1-antitrypsin deficiency)
- Consume excessive amounts of alcohol (Michigan Alcohol Screening Test score  $>$  4) 
- Have a history of known cardiovascular, pulmonary or renal disease
- Diagnosed T1DM or T2DM
- Are not weight stable for 3 months prior to the beginning of study (weight gain or loss  $>$  4 kg)
- Are claustrophobic or have implanted metallic/electrical devices (e.g. cardiac pacemaker, neuro-stimulator)
- Are not able to keep a food diary or activity log for 7 consecutive days
- Are taking drugs that induce steatosis (e.g. corticosteroids, estrogens, methotrexate, Ca channel blockers)
- Are taking drugs that benefit NAFLD (e.g. betaine, pioglitazone, rosiglitazone, metformin, or gemfibrozil)
- Are taking drugs that influence study outcomes (weight loss, lipid-lowering, glucose-lowering medications)
- Are perimenopausal or have an irregular menstrual cycle (menses that does not appear every 27-32 days)
- Are pregnant, or trying to become pregnant
- Are smokers

